#### 9.2.4.1 Reporting Timeframes to Clinical Director, and/or NIH Intramural IRB

##### Serious Events

**Reports to the IRB and CD:** The PI must report Serious UPs, and Serious PDs to the IRB and CD as soon as possible but not more than 7 days after the PI first learns of the event via the NIH Problem Report Form.

**Reports to the CD:** The PI must report all SAEs that do not meet the definition of UP to the CD not more than 14 days after the PI first learns of the event.

### **Non-serious Events**

*Reports to the IRB and CD:* The PI must report all UPs that are not Serious to the IRB and CD, and PDs that are not Serious to the IRB, not more than 14 days after the PI first learns of the event via the NIH Problem Report Form.

### **Deaths**

The PI must report all deaths (that are not UPs) to the CD as soon as possible, but not more than 7 days after the PI first learns of the event.

#### **9.2.4.2 At continuing review, the PI will provide to the IRB a summary of:**

- All UPs
- All PDs
- All AEs (except for those granted a waiver of reporting)
- If, while preparing the continuing review, the PI identifies a greater frequency or level of severity of expected adverse events than was previously identified in the protocol or investigational brochure (IB), these should be reported separately as a UP. If such an observation occurs before the time of continuing IRB review, it should be reported to the IRB and CD as a UP in the time frames noted above and summarized at the time of continuing review.

#### **Exclusions to data reporting:**

The following Adverse Events will be captured only in the source documents and will not be reported to the IRB at the time of continuing review.

- Laboratory values that do not meet the definition of AE listed in Section 9.2.2.
- All grade 1 events listed as expected in the investigator's brochure, package insert, and/or anticipated events.
- In view of the underlying illness, MDS, all patients will enter the study with abnormally low blood counts that would meet criteria as grade 3 or more commonly grade 4 toxicity, and requiring frequent platelet and/or red cell transfusions, and thus AEs regarding hematologic lab values including thrombocytopenia or platelet-transfusion dependence, anemia or red cell transfusion dependence, neutropenia, lymphopenia, or leukopenia will not be evaluable. Thus, we will collect hematologic laboratory values in the subject's source documents, but will not record or report these abnormalities as adverse events.

In addition, the following non-hematologic AEs will be captured only in the source documents and will not be reported to the IRB at the time of continuing review:

- Because eltrombopag (Promacta®) is an FDA approved drug with known toxicity profiles, any observed or volunteered adverse events that are listed on the package insert will not be reported unless (1) the adverse event is previously unknown (not on the package insert); (2) the adverse event is more severe than on the package insert; or (3) meets the criteria for a serious adverse event. The collection of AEs information will begin on the first day of initiation of therapy.

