### 4. ELIGIBILITY ASSESSMENT

#### 4.1 Inclusion criteria

- 4.1.1 Diagnosis of MDS, with WHO classification of refractory anemia, refractory cytopenia with unilineage dysplasia (RCUD), RARS, RCMD-RS, or RCMD
- 4.1.2 IPSS risk scores of low, intermediate-1, or intermediate-2.
- 4.1.3 Platelet count  $\leq 30,000/\mu\text{L}$  or platelet-transfusion-dependence (requiring at least 4 platelet transfusions in the 8 weeks prior to study entry); OR hemoglobin less than 9.0 gr/dL or red cell

- transfusion-dependence (requiring at least 4 units of PRBCs in the eight weeks prior to study entry) OR ANC $\leq$ 500
- 4.1.4 Age  $\geq$  18 years old
  - 4.1.5 Treatment naïve or off all other treatments for MDS (except stable dosing of filgrastim (G-CSF), erythropoietin, and transfusion support) for at least four weeks. G-CSF can be used before, during and after the protocol treatment for subjects with documented neutropenia (<500/UL) as long as they meet the criteria for other cytopenias as stated above. G-CSF must be held for 3 weeks prior to enrollment bone marrow biopsy and prior to each study assessment bone marrow biopsy, unless clinically indicated to avoid infections per PI discretion.
  - 4.1.6 Adequate liver function, as evidenced by total serum bilirubin  $\leq$  1.5 times the upper limit of normal (patients with Gilbert's disease are eligible, provided intermittent indirect hyperbilirubinemia, AST or ALT  $\leq$  5 times the upper limit of normal).
  - 4.1.7 A serum creatinine concentration  $\leq$  2 x ULN

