### 5.2 Dose Adjustments (increases/decreases) of Eltrombopag (See section 2.6)

Patients will be enrolled on study because of anemia and/or thrombocytopenia. The majority of patients are expected to have cytopenias in both cell lines lineages, however some patients will have normal or close to normal counts in one or the other lineage at baseline. Therefore, dose adjustment criteria will vary depending on whether one or both lineages meet inclusion criteria, however dose adjustment will occur via the tables below and continue to the maximum dose until the inclusion criterion lineage or lineages responds, according to the schema set out below, unless toxicity-related stopping or dose reduction lab values occur. Note that patients entering the study based on anemia, with normal or near normal platelet count, will be expected to have an increased

in their platelet count on eltrombopag, but dose escalation for anemia will not be halted unless the platelet count goes above 400,000/ $\mu$ L. For patients entering meeting both anemia and thrombocytopenia eligibility criteria, dose escalation will not stop until both lineages reach the thresholds given below to stay on the current dose, unless platelets go over 400,000/ $\mu$ L or hemoglobin goes over 16.0 gr/dL, in which case drug will be discontinued for one week and the dose decreased by 50%. If the stopping platelet count or hemoglobin is reached regardless of entry criteria eltrombopag will be discontinued for one week and restarted at the next lowest dose.

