#### 9.2.2 Adverse Events Management:

All adverse events occurring during the study, including those observed by or reported to the research team, will be recorded. The AEs will be graded by severity utilizing CTCAE version 4.0. A copy of the criteria can be down-loaded at [http://evs.nci.nih.gov/ftp1/CTCAE/CTCAE\\_4.03\\_2010-06-14\\_QuickReference\\_8.5x11.pdf](http://evs.nci.nih.gov/ftp1/CTCAE/CTCAE_4.03_2010-06-14_QuickReference_8.5x11.pdf).

Eltrombopag has known and unknown toxicity profiles, thus, any observed or volunteered adverse events that are as listed in the Package Insert and/or Investigator's Brochure will not be reported unless (1) the adverse event was not present at baseline exam; (2) the adverse event is previously unknown (not on the label); (3) the adverse event is more severe than on the label; (4) the frequency of the adverse events increases above the listed frequency; or (5) meets the criteria for a serious adverse event.

**Non-hematologic abnormal laboratory findings** used to evaluate the safety of this protocol regimen will be collected to include any change from laboratory assessments done prior to first dose of eltrombopag that result in a progression to a grade 3 or 4 laboratory toxicity and/or are characterized by any of the following:

- Results in discontinuation from the study
- Is associated with clinical signs or symptoms
- Requires treatment or any other therapeutic intervention
- Is associated with death or another serious adverse event, including hospitalization
- Is judged by the Investigator to be of significant clinical impact
- If any abnormal laboratory result is considered clinically significant, the investigator will provide details about the action taken with respect to the test drug and about the patient's outcome.

In view of the underlying illness (bone marrow failure), many patients may enter the study with compromised hematologic indices that would be classified as toxicities. Therefore, we will look

at the relative decline of hematologic parameters and length of time to recovery to the patient's baseline as more significant than absolute values of these parameters. The laboratory toxicities will be graded by severity utilizing CTCAE version 4.0 or as mild, moderate, severe or life threatening according to the tables below:

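### The rule that no blood-count abnormality is recorded as an adverse event rests on a premise that does not cover lineages normal at entry, and it conflicts with section 9.2.2

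*Combined protocol and SAP*

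**What the plan says.** Section 9.2.4.2, under Exclusions to data reporting, gives its reason as "all patients will enter the study with abnormally low blood counts that would meet criteria as grade 3 or more commonly grade 4 toxicity". It concludes that events concerning thrombocytopenia, anemia, neutropenia, lymphopenia or leukopenia cannot be evaluated. The values go into source documents, "but will not record or report these abnormalities as adverse events". No condition is set on lineage or baseline count. The lead-in to the list is narrower and concerns reporting at continuing review: "The following Adverse Events will be captured only in the source documents and will not be reported to the IRB".

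Other sections describe baseline and recording differently:

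- **Section 4.1.3** joins the platelet, red cell and neutrophil criteria by OR; the second begins "OR hemoglobin less than 9.0 gr/dL or red cell". One qualifying lineage is enough.
- **Section 5.2** expects that "some patients will have normal or close to normal counts in one or the other lineage at baseline", and mentions "patients entering the study based on anemia, with normal or near normal platelet count".
- **Section 9.2.2** says that all adverse events are recorded. It says only that many subjects, not all, may enter with compromised counts, and that the study will look at the "relative decline of hematologic parameters and length of time to recovery" to the subject's own baseline.
- **Section 8.2** measures the toxicity profile by CTCAE version 4.0.

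**The concern.** An exclusion for low counts makes sense where the count is already at the bottom of the grading scale at entry, because a further fall cannot be graded. The argument fails for a lineage that starts normal or near normal. There a new severe cytopenia is plainly evaluable, and it is one of the things a safety assessment in a marrow disorder should show.

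Safety is assessed alongside the primary objective, and toxicity during extended treatment is a secondary objective (section 8.1). If staff follow section 9.2.4.2, these events do not reach the adverse event record. They are then also absent from what is built on it: the event summary for the DSMB (9.2.4.3) and the annual summary of non-serious events for the sponsor and FDA (9.2.4.4). If staff follow section 9.2.2, the events are recorded. The same laboratory finding can therefore be handled in two ways, each with support in the protocol.

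**Working it through.** The plan gives no figure on this point, so the check compares the texts and follows one case through them.

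**Step 1. Does the premise cover the exclusion?**

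- The exclusion covers five kinds of low count (platelets, hemoglobin, neutrophils, lymphocytes, leukocytes) in every subject.
- Eligibility (4.1.3) guarantees one low lineage or transfusion dependence, out of three lineages. Lymphocytes and total leukocytes are not entry criteria.
- Section 5.2 expects some subjects to be normal or near normal in hemoglobin or in platelets.

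The premise therefore supports the exclusion for the lineage or lineages that are severely low at entry, and not for the rest. CTCAE cut-offs are not in the documents, so nothing here depends on whether a hemoglobin just under 9 g/dL is grade 3.

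**Step 2. Follow a case.** A subject enrols on anemia alone with normal platelets, then develops a severe, asymptomatic fall in platelets.

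| Section | Handling of the fall in platelets |
|---|---|
| 9.2.1 | An abnormal laboratory finding is within the adverse event definition |
| 9.2.2 | Recorded and graded; decline from baseline and recovery examined |
| 9.2.4.2 | Value kept in source documents; not an adverse event |

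The second and third rows cannot both be followed.

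**Step 3. What other routes capture it?**

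- Counts: the blood count is repeated within 72 hours of the first dose (6.1), taken weekly to week 16 (6.2) and then every 1 to 3 months in extended access (6.3). Home laboratory values are entered in the data system (9.4).
- Discontinuation: section 5.4.2 acts on significant worsening of anemia or neutropenia, and section 8.6.2 lists new or worsening cytopenias. These cases can be counted.
- Serious events are collected throughout (9.2.3), although admission simply to receive a transfusion is not reported as serious.
- Bleeding of grade 2 or higher is a secondary endpoint (8.2).

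What remains uncaptured as an event is the new laboratory cytopenia that is not serious and leads to neither bleeding nor discontinuation.

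**Step 4. Does a planned analysis fill the gap?** Section 9.2.2 states an intention to look at decline and recovery but gives no threshold, summary measure or table. Section 8.4 contains no such analysis.

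**Step 5. Grade IV hematologic toxicity.** Section 8.5 counts related Grade IV toxicity toward the study stopping rule and excludes only readily reversible metabolic or laboratory abnormalities. Section 8.6.2 uses similar wording for individual discontinuation but also excludes hematologic toxicities. With section 9.2.4.2 keeping laboratory cytopenias out of the event record, the documents do not settle whether such an event can count under section 8.5.

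**The case against.** The strongest defence is that the sections work together. Section 9.2.2 already separates hematologic from other laboratory findings and prefers change from baseline to absolute grades, which is reasonable in MDS. Section 9.2.4.2 sits under the summary given to the IRB, so it could be read as limiting that report and nothing else. The counts are kept, worsening counts lead to action, and serious events and bleeding are collected. Section 5.2 also expects most subjects to be low in both hemoglobin and platelets.

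Much of this stands, and it rules out three stronger readings that a reader might infer.

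- **That hematologic toxicity disappears from the study or is zero by rule.** It does not. The exclusion concerns laboratory values recorded as events, and the routes in step 3 remain.
- **That section 5.2 expects subjects with normal counts overall.** It refers to one or the other lineage; each subject still has a qualifying low lineage or transfusion dependence.
- **That the uncounted cytopenias would be caused by the drug.** In a single-arm MDS study a falling count may reflect the disease, and the documents give no share attributable to eltrombopag.

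The defence does not remove the conflict. The sentence on hematologic values bars recording as well as reporting, so the IRB-only reading does not fit it. An intention to look at decline, with no table, does not replace an event record.

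**Conclusion.** The rule is wrong as written, rather than merely short of detail, and should be changed. Its premise does not reach lineages that are normal or near normal at entry, and it contradicts section 9.2.2. The consequence is that new, non-serious laboratory cytopenias in those lineages would be absent from the CTCAE-based adverse event table, while the underlying counts are kept.

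The size cannot be computed, because the documents do not give the share of subjects with a normal lineage or the rate of new cytopenias. From section 5.2, those with normal or near-normal hemoglobin or platelets should be a minority; it gives no expectation for neutrophils. The efficacy test and the numerical stopping boundaries do not change. Whether the event count fed into those boundaries is affected depends on the unresolved wording in sections 8.5 and 8.6.2, and the documents support no figure for it.

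The conclusion assumes that section 9.2.4.2 would be followed literally. If staff in practice record these events under section 9.2.2, the fault is confined to the text.

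**What to change.** 1. In section 9.2.4.2, limit the exclusion to lineages already at grade 3-4, or transfusion dependent, at baseline. Use the blood count taken within 72 hours of the first dose to classify each lineage.
2. Record new grade 3-4 cytopenias in all other lineages as adverse events, and align the wording with section 9.2.2. Say explicitly that the source-documents-only lead-in limits IRB reporting and not entry in the study database.
3. Add to section 8.4 a table per lineage, split by baseline status, with the maximum relative decline and the time to recovery to baseline. Use the blood counts already collected, and state how counts after transfusion are handled.
4. Reconcile sections 8.5 and 8.6.2 on whether Grade IV hematologic toxicity counts. If they are meant to differ because one governs the study and the other the individual, say so.

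The cost is protocol wording, one table and a few more adverse event entries. No extra visit or sample is needed.

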#### **9.2.4.3 NHLBI DSMB Reporting:**

Reports of serious adverse events that are unexpected and thought to be related to the experimental drug will also be forwarded as soon as possible but no later than seven (7) days in the case of death or life-threatening serious adverse events or within fifteen (15) days after the occurrence of all other forms of serious adverse event to the Data and Safety Monitoring Board (DSMB). A summary of events will be included in DSMB reports for review by the DSMB.

#### **9.2.4.4 Sponsor and FDA Reporting**

IND # 105,207

Sponsor: NHLBI OCD

A summary of all SAEs, non-serious AEs, and other events will be recorded and submitted to the Sponsor and FDA in annual progress reports (21 CFR 312.64(b)).

The PI will report SAEs to the Sponsor according to the requirements of 21 CFR 312.64(b) and as agreed upon with the sponsor. The Sponsor (or designee) will determine the reportability of the event to the FDA and IND safety report will be submitted to the FDA as required. The PI or designee will report SAEs to the Sponsor within 24 to 72 hours of discover.

#### **IND Safety Reports to the FDA (Refer to 21 CFR 312.32)**

The sponsor must notify FDA in an IND safety report of potential serious risks, from clinical trials or any other source, as soon as possible, but in no case later than 15 calendar days after the sponsor determines that the information qualifies for reporting. The sponsor must also notify FDA of any unexpected fatal or life-threatening suspected adverse reaction as soon as possible but in no case later than 7 calendar days after the sponsor's initial receipt of the information.

#### *15-day reporting*

The sponsor must report any suspected adverse reaction that is both serious and unexpected. The sponsor must report an adverse event as a suspected adverse reaction only if there is evidence to suggest a causal relationship between the drug and the adverse event, such as:

- A single occurrence of an event that is uncommon and known to be strongly associated with drug exposure (e.g., angioedema, hepatic injury, Stevens-Johnson Syndrome);
- One or more occurrences of an event that is not commonly associated with drug exposure, but is otherwise uncommon in the population exposed to the drug (e.g., tendon rupture);
- An aggregate analysis of specific events observed in a clinical trial (such as known consequences of the underlying disease or condition under investigation or other events that commonly occur in the study population independent of drug therapy) that indicates those events occur more frequently in the drug treatment group than in a concurrent or historical control group

The sponsor must submit each IND safety report in a narrative format or on FDA Form 3500A.

FDA contact:

Division of Drug Oncology Products, Office of Drug Product  
CDER Therapeutic Biological Products  
Document Control Center  
Center for Drug Evaluation and Research, Food and Drug Administration  
[name]  
[contact]

### 9.3 Reporting of pregnancy

Subjects who become pregnant during the study should discontinue the study immediately. The investigator, or his/her designee, will collect pregnancy information on any subject who becomes pregnant while participating in this study. The investigator, or his/her designee, will submit pregnancy information to the DSMB, IRB, FDA and Novartis within two weeks of learning of a subject's pregnancy. Information on the status of the mother and child will be forwarded to the DSMB, IRB, FDA and Novartis. Generally, follow-up will be no longer than 6 to 8 weeks following the estimated delivery date. Any premature termination of the pregnancy will be reported. While pregnancy itself is not considered to be an AE or SAE, any pregnancy complication or elective termination of a pregnancy for medical reasons will be recorded and reported to the DSMB, IRB, FDA and Novartis as an AE or SAE. A spontaneous abortion is always considered to be an SAE and will be reported to the DSMB, IRB, FDA and Novartis. Furthermore, any SAE occurring as a result of a post-study pregnancy and is considered reasonably related to the investigational product by the investigator, will be reported to the DSMB, IRB, FDA and Novartis. While the investigator is not obligated to actively seek this information in former study participants, he/she may learn of an SAE through spontaneous reporting.

### 9.4 Data management

#### **Data management**

The PI will be responsible for overseeing entry of data into an in-house password protected electronic system and ensuring data accuracy, consistency and timeliness. The principal investigator, associate investigators, research nurses and/or a contracted data manager will assist with the data management efforts. Data will be abstracted from Clinical Center progress notes as well as from progress notes forwarded from the home physician. Laboratory values from referring home physicians will be entered into the system. All human subjects personally identifiable information (PII) eligibility and consent verification will be recorded. Primary data obtained during the conduct of the protocol will be kept in secure network drives or in approved alternative sites that comply with NIH security standards. Primary and final analyzed data will have identifiers so that research data can be attributed to an individual human subject participant, e.g., unique code or minimum PII required for subject identification.

In order to maintain patient confidentiality, all communications relating to the study will identify participants by assigned subject study numbers. No personally identifiable information will be sent to the DSMB, IRB, FDA or Novartis. The US Food and Drug Administration (FDA) may also request access to all study records, including source documentation for inspection.

**End of study procedures:** Data will be stored in locked cabinets and in a password protected database until it is no longer of scientific value.

**Loss or destruction of data:** Should we become aware that a major breach in our plan to protect patient confidentiality and trial data has occurred, the IRB will be notified.

**Publication Policy:** Given the research mandate of the NIH, patient data including the results of testing and responses to treatment will be entered into an NIH-authorized and controlled research database. Any future research use will occur only after appropriate institutional approval.

No identifiable data will be sent outside NIH without IRB notification and an executed MTA or CTA.

A Clinical Trials Agreement (CTA) with Novartis is in place to support this study.

